#### INTRODUCTION

Intermittent exotropia (XT), is the commonest type of exodeviation, and represents about 44.7% of all childhood exotropia[1]. Intermittent XT is classified into basic, true divergence excess, pseudo-divergence excess, and convergence insufficiency (CI) type [2, 3] The basic type where the deviation is similar at distance and near, is the most common subtype [4]

For basic XT, the choice of surgical procedure is still controversial. Many strabismologists prefer bilateral recession surgery (BLR) while others prefer unilateral recess-resect (RR) surgery [5-9]. The choice between either strategy depends on many factors including ocular dominance and surgical experience. Surgeons weight advantages of each procedure including easier surgical manipulations for BLR and higher success rates of the R-R procedure against drawback of each procedure including higher rate of recurrence in BLR versus higher rate of consecutive esotropia and lateral incomitance for R-R procedure [4, 10-13].

Despite ocular dominance is an important factor affecting long term results of surgery, no standard surgical procedure has been suggested for exotropic patients with a dominant eye. Some studies suggested the R-R procedure on the non-dominant eye for basic XT [2, 7, 10], while others suggested BLR, asymmetrical with more recession in the deviating non-dominant eye [14, 15] or symmetrical without considering effect of ocular dominance on surgical decision [16, 17].

In our study, we will compare long term motor and sensory effects of symmetric and asymmetric BLR recession in treatment of basic XT with a dominant eye.

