#### AIM OF THE WORK

To study the clinical safety and efficacy of Symmetric versus asymmetric bilateral lateral rectus recession in management of basic intermittent exotropia with ocular dominance.

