## PATIENTS AND METHODS

This is a prospective study including patients diagnosed as basic intermittent exotropia with a dominant eye in the strabismus unit, ophthalmology department, Benha University Hospital. Written informed consent will be provided by legal guardian of each patient before inclusion in the study.

These patients will undergo complete ophthalmologic and orthoptic examinations before surgery including BCVA, cycloplegic refraction, state of ocular dominance and ocular motility assessment. The angle of deviation at far and near is measured with the prisms and alternating cover test. Eye dominance was determined with the alternative cover test. Sensory testing was performed using the Titmus stereo test and the Worth 4-Dot test at distance and near.

Patients with a history of orbital or scleral buckle surgery, and those with incomitant strabismus including thyroid eye disease, myasthenia gravis, Duane syndrome, cranial nerve palsies and patient with any degree of preoperative limitation of ductions were excluded. Besides, patients with a preoperative A or V-pattern, dissociated vertical deviation, or oblique muscle overactions were also excluded.

3

Patients will be randomized into two groups. The first group, referred to as the symmetric bilateral rectus recession group (S-BLR group). The other group, referred to as the asymmetric bilateral rectus recession group (A-BLR group).

In the S-BLR group, the amount of recession, based on the largest angle of exodeviation measured before surgery, was symmetrically divided between two eyes guided by standard strabismus surgical tables. In A-BLR group, the amount of recession in the non-dominant eye will be 2 mm more than in the dominant eye.

Postoperative measurements will be performed in the same way as the preoperative ones, at one week, one month, three months, six months, one year, and later at six months intervals after surgery. Outcome parameters at one year after surgery will be used for comparisons and analysis. Satisfactory outcome is defined as between 10 PD of exophoria/tropia and 10 PD of esophoria/tropia at one year after surgery. Recurrence is considered if alignment is more than 10 PD of exophoria/tropia, while overcorrection is considered if alignment is more than 10 PD of esophoria/tropia.

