# STATISTICAL ANALYSIS

Statistical analyses were performed using SPSS software version 17.0 (SPSS Inc, Chicago, IL). The pre- and postoperative values are described as means plus or minus standard deviations. The data were compared using the *t* test with a P value of < .05 was considered statistically significant.

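### The promised sensory comparison has no defined endpoint, and the only stated analysis (mean ± SD and a t test) does not suit Worth 4-Dot, Titmus or the motor outcome categories

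*Combined protocol and SAP*

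**What the plan says.** **Objective.** The Introduction puts sensory effects beside motor effects: "we will compare long term motor and sensory effects of symmetric and asymmetric BLR recession". The section Aim of the Work is more general: "To study the clinical safety and efficacy of Symmetric versus asymmetric bilateral lateral rectus recession".

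**Data.** Patients and Methods names two sensory instruments: "Sensory testing was performed using the Titmus stereo test and the Worth 4-Dot test at distance and near". After surgery, "Postoperative measurements will be performed in the same way as the preoperative ones", at each scheduled visit. Sensory tests are thus covered by implication, not by name.

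**Time point.** "Outcome parameters at one year after surgery will be used for comparisons and analysis". The parameters are not listed.

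**Defined outcomes.** There are three, all in prism dioptres. The first is success: "Satisfactory outcome is defined as between 10 PD of exophoria/tropia and 10 PD of esophoria/tropia at one year after surgery". The other two are failures in either direction: "Recurrence is considered if alignment is more than 10 PD of exophoria/tropia, while overcorrection is considered if alignment is more than 10 PD of esophoria/tropia".

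**Analysis.** The Statistical Analysis section is three sentences. It names the software, states that "The pre- and postoperative values are described as means plus or minus standard deviations", and gives a t test at the 5% level. It does not say whether the test is paired or two-sample, and it names no method for categorical, ordinal or ranked data.

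**The concern.** An objective is stated and the data for it are to be collected, but two links are missing between them: a defined endpoint and a suitable analysis.

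- **Worth 4-Dot** sorts patients into categories such as fusion, suppression or diplopia. Mean ± SD does not describe categories.
- **Titmus** moves in unequal steps of seconds of arc and is right-skewed. A patient with no measurable stereopsis has no score. Before a mean can be taken, someone must drop that patient or assign a number, and the plan does neither.
- **Satisfactory outcome, recurrence and overcorrection** are categories too. The mean signed angle does not replace them: a value near zero can arise when all patients are well aligned, or when recurrences and overcorrections cancel.

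What is at stake is the credibility of any sensory claim. Its scoring, its handling of nil results and its test would be chosen after the data are seen, and those choices can change the size and even the direction of the reported difference.

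**Working it through.** **Nothing to reproduce.** The documents give no sample size, effect size, SD, event rate or dropout rate. All inputs below are assumptions, used only to see how far the unstated choices can matter.

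**1. Objective against endpoint.** Motor effects: three definitions, all in prism dioptres. Sensory effects: no threshold, no scoring rule, no definition of improvement or loss.

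**2. One poor Titmus result.** Assume a scale from 40 to 3000 seconds of arc and 20 patients, 19 at 60 and one at 3000.
- Arithmetic mean: (19 × 60 + 3000)/20 = 4140/20 = 207.
- Geometric mean: 10^((19 × 1.778 + 3.477)/20) = 10^1.863 ≈ 73.
- If that patient instead has nil stereopsis and is dropped: mean = 60.

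**3. Two arms with a nil category.** Assume these proportions at 40, 60, 100, 200, 400, 800, 3000 and nil:
- Arm A: 0.20, 0.20, 0.20, 0.10, 0.08, 0.05, 0.07, 0.10.
- Arm B: 0.08, 0.12, 0.20, 0.22, 0.16, 0.10, 0.07, 0.05.

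Lower is better. The medians are 100 (A) and 200 (B). The scored levels contribute 8 + 12 + 20 + 20 + 32 + 40 + 210 = 342 to A's mean and 3.2 + 7.2 + 20 + 44 + 64 + 80 + 210 = 428.4 to B's.

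| Handling of nil | Mean A | Mean B | Lower mean |
|---|---|---|---|
| Dropped | 342/0.90 = 380 | 428.4/0.95 = 451 | A |
| Coded 3000 | 342 + 300 = 642 | 428.4 + 150 = 578 | B |
| Coded 5000 | 342 + 500 = 842 | 428.4 + 250 = 678 | B |
| Coded 10000 | 342 + 1000 = 1342 | 428.4 + 500 = 928 | B |

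The drop-or-code choice alone reverses which arm has the better mean. Simulated power at 50 per arm, over the three codings, was 0.06–0.11 for a t test on raw seconds, 0.11–0.17 for a t test on log seconds, and 0.38–0.39 for Mann-Whitney. Once nil ranks below every scored level, a rank result does not depend on the number given to it.

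**4. Is a t test on a yes/no sensory result invalid?** Exact two-sided type I error of a two-sample t test on fusion coded 0/1, for 20, 30 or 50 per arm and true rates of 0.5, 0.7 or 0.9, ran from 0.039 to 0.057. That is close to the nominal 0.05, so such a comparison could be run.

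**5. Scale of a binary sensory comparison.** With n per arm = [1.96 √(2p̄(1−p̄)) + 0.842 √(p₁(1−p₁) + p₂(1−p₂))]² / (p₁−p₂)², where p̄ is the average of the two rates (two-sided 5%, 80% power, equal arms):
- 50% vs 70%: [1.96 × 0.693 + 0.842 × 0.678]²/0.04 → 93 per arm.
- 60% vs 80%: 82 per arm.
- 70% vs 85%: 121 per arm.

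The plan states no sample size to set against these.

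**The case against.** The strongest reply is that the plan is brief, not broken. Patients and Methods names both sensory tests, implies their repetition after surgery, fixes one year as the comparison point and randomises two groups. The data should exist and the contrast is clear. A t test on log seconds or on 0/1 fusion could be run, and step 4 shows acceptable error rates for the latter. Sensory effects appear as an objective only in the Introduction; Aim of the Work speaks of safety and efficacy. All of this stands, and it limits what can be claimed.

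Four stronger readings are tempting, and the documents do not support them:

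- **That the sensory question cannot be answered.** Measurement and a one-year comparison are planned. What is missing is prespecification and a suited method.
- **That nil results will be dropped, making a worse arm look better.** No section says so. The plan is silent, and the risk comes from that silence.
- **That a within-arm before-and-after test is planned.** The sentence on pre- and postoperative values concerns description. The test is named separately, without saying paired or two-sample, and the Introduction frames the contrast as symmetric versus asymmetric recession.
- **That the success definition conceals sensory loss.** It is an alignment rule and is not said to be the only outcome. Cross-tabulating success against sensory loss would be an optional extra.

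The examples also rest on chosen inputs. In step 3, arm A has the better median but more nil results, so the raw mean is not simply wrong there. It answers a different question, and the unstated code for nil fixes its value.

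What the objection does not remove is that the one method the plan states for all its data fits neither sensory instrument nor the three motor categories.

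**Conclusion.** The concern holds as a gap between objective, endpoint and analysis. A sensory comparison is promised and its data are collected, but no sensory endpoint is defined, and mean ± SD with a t test does not suit a categorical test or a stepped, skewed scale with an unscored worst level. The motor categories share the problem, so the gap is not confined to the sensory half.

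Its size cannot be taken from the documents. The 207, 73 and 60 seconds of arc, the reversal of the arm means and the power figures rest on the assumed distributions above. They show that the unstated choices can matter, not that they will in this trial. The point should be corrected before analysis. It does not make the trial uninformative.

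**What to change.** Amend Patients and Methods and Statistical Analysis as follows.

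1. State by name that Titmus and Worth 4-Dot (distance and near) are repeated after surgery. List their one-year results as secondary endpoints compared between the randomised arms.
2. **Titmus:** analyse the one-year level as an ordered category, with nil stereopsis kept as the worst level, by an ordinal or rank method adjusted for the baseline level (for example, ordinal logistic regression). Use the one-year level, not change from baseline: differences between ordered categories have no fixed size, and a patient with nil at baseline cannot worsen. Record untestable separately from nil.
3. **Worth 4-Dot:** define which responses count as fusion, suppression and diplopia. Report fusion at distance and at near as n (%) per arm, with a difference in proportions, 95% CI and a chi-square or Fisher exact test.
4. **Motor categories:** report satisfactory outcome, recurrence and overcorrection in the same way. Keep mean ± SD and a two-sample t test for the angle itself.

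**Cost.** Wording only; no new test, visit or treatment. There are two small downsides. Several secondary comparisons without multiplicity control must be read as supportive, the more so because no sample size is stated. Patients untestable at baseline will contribute less to the sensory analysis.

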#### AIM OF THE WORK

To study the clinical safety and efficacy of Symmetric versus asymmetric bilateral lateral rectus recession in management of basic intermittent exotropia with ocular dominance.

## PATIENTS AND METHODS

This is a prospective study including patients diagnosed as basic intermittent exotropia with a dominant eye in the strabismus unit, ophthalmology department, Benha University Hospital. Written informed consent will be provided by legal guardian of each patient before inclusion in the study.

These patients will undergo complete ophthalmologic and orthoptic examinations before surgery including BCVA, cycloplegic refraction, state of ocular dominance and ocular motility assessment. The angle of deviation at far and near is measured with the prisms and alternating cover test. Eye dominance was determined with the alternative cover test. Sensory testing was performed using the Titmus stereo test and the Worth 4-Dot test at distance and near.

Patients with a history of orbital or scleral buckle surgery, and those with incomitant strabismus including thyroid eye disease, myasthenia gravis, Duane syndrome, cranial nerve palsies and patient with any degree of preoperative limitation of ductions were excluded. Besides, patients with a preoperative A or V-pattern, dissociated vertical deviation, or oblique muscle overactions were also excluded.

3

Patients will be randomized into two groups. The first group, referred to as the symmetric bilateral rectus recession group (S-BLR group). The other group, referred to as the asymmetric bilateral rectus recession group (A-BLR group).

In the S-BLR group, the amount of recession, based on the largest angle of exodeviation measured before surgery, was symmetrically divided between two eyes guided by standard strabismus surgical tables. In A-BLR group, the amount of recession in the non-dominant eye will be 2 mm more than in the dominant eye.

Postoperative measurements will be performed in the same way as the preoperative ones, at one week, one month, three months, six months, one year, and later at six months intervals after surgery. Outcome parameters at one year after surgery will be used for comparisons and analysis. Satisfactory outcome is defined as between 10 PD of exophoria/tropia and 10 PD of esophoria/tropia at one year after surgery. Recurrence is considered if alignment is more than 10 PD of exophoria/tropia, while overcorrection is considered if alignment is more than 10 PD of esophoria/tropia.

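### Does the asymmetric arm's bare 2 mm rule leave total recession confounded with asymmetry?

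*Combined protocol and SAP*

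**What the plan says.** Patients and Methods gives the symmetric arm a full rule. The amount is "based on the largest angle of exodeviation measured before surgery, was symmetrically divided between two eyes guided by standard strabismus surgical tables". The next sentence defines the other arm by contrast: "In A-BLR group, the amount of recession in the non-dominant eye will be 2 mm more than in the dominant eye". It names no angle, table or total, and does not say which eye, if either, receives the table amount.

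The Introduction states the question as a comparison of two ways of dividing the surgery: "we will compare long term motor and sensory effects of symmetric and asymmetric BLR recession". Allocation is random ("Patients will be randomized into two groups") and the comparison is made at one year ("Outcome parameters at one year after surgery will be used for comparisons and analysis"). Statistical Analysis offers one method: "The data were compared using the *t* test with a P value of < .05 was considered statistically significant". It plans no adjustment for millimetres of recession and no analysis per millimetre.

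**The concern.** A difference between two numbers fixes neither of them. Taken alone, the asymmetric-arm sentence allows a total equal to, above or below that of the symmetric arm. If the totals differed, the arms would differ in two respects at once: how the recession is divided, and how much is done. A significant result could then be reported as an effect of asymmetry when asymmetry does nothing. Equally, opposite effects of amount and division could cancel. The t test could not separate these cases. The Introduction does not settle it either. Its phrase "asymmetrical with more recession in the deviating non-dominant eye" says only which eye gets more, and it describes what other studies suggested, not this trial's arm.

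**Working it through.** **What the documents supply.** They state no sample size, SD, effect size or PD per mm, so there is no planned figure to reproduce. The inputs taken from the text are the 2 mm difference and the unadjusted t test at P < .05 (two-sided assumed). Everything else below is an assumption.

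**Step 1: totals under each simple reading.** Let R be the table amount per eye, so the symmetric total is 2R. These are readings of the text, not proposals.

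| Dominant eye | Non-dominant eye | Total | Difference from symmetric arm |
|---|---|---|---|
| R − 1 | R + 1 | 2R | 0 mm |
| R | R + 2 | 2R + 2 | +2 mm |
| R − 2 | R | 2R − 2 | −2 mm |

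**Step 2: what a 2 mm gap would do to the planned test.** Assume k = 1, 2 or 3 PD per mm of total recession, so the shift is d = 2k = 2, 4 or 6 PD. Assume 30 per arm and no effect of asymmetry. The chance of significance comes from the noncentral t distribution with 58 degrees of freedom and noncentrality d / (SD × √(2/30)). For d = 4 and SD = 8 this is 4 / (8 × 0.258) = 1.94.

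| Shift | SD 6 | SD 8 | SD 10 |
|---|---|---|---|
| 0 PD | 5.0% | 5.0% | 5.0% |
| 2 PD | 24.6% | 15.9% | 11.9% |
| 4 PD | 71.9% | 47.8% | 33.2% |
| 6 PD | 96.8% | 81.5% | 62.8% |

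These are error rates only for a claim about asymmetry. For the question of whether the two procedures, as performed, give different alignment, they are power to detect a real difference.

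**Step 3: which reading the text supports.** The symmetric-arm sentence speaks of a single amount, set from the largest angle and the tables, and of dividing it between two eyes. The following sentence changes only the division. Read together, one amount is split equally in one arm and with a 2 mm difference in the other. That is the first row of Step 1, and the zero row of Step 2. Nothing in the documents says that the totals differ.

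**Step 4: whether a per-millimetre analysis would help if they did differ.** Assume angles uniform on 20–45 PD (mean 32.5), R rising linearly from 5 to 9 mm (mean 7, total 14), full correction on average in the symmetric arm, SD 8, 30 per arm and no effect of asymmetry. Average correction per mm is then 32.5 / 14 = 2.32 PD. Let the extra 2 mm act at k PD per mm. At the mean angle the larger-total arm corrects (32.5 + 2k) / 16 PD per mm: 2.16 for k = 1, 2.28 for k = 2 and 2.41 for k = 3. The ratio therefore differs between arms unless k is near 2.32. Simulated rates of a significant result, over totals 2 mm higher and 2 mm lower:

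| k (PD per mm) | Planned t test | t test on PD corrected per mm |
|---|---|---|
| 1 | 16–17% | 19–25% |
| 1.5 | 29–30% | 10–13% |
| 2 | 47–48% | 5–6% |
| 3 | 81–82% | about 10% |

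The ratio test keeps its 5% level only when the marginal effect of a millimetre is close to the average effect. At the low end of the assumed range it does worse than the planned test. Entering total millimetres as a covariate also fails, because within each arm millimetres track the angle. In a simulation with correction proportional to total millimetres and totals 2 mm apart, the covariate-adjusted test was significant in 34–77% of trials, against 42–84% unadjusted.

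**The case for a change.** The strongest case for a change is that the equal-total rule is nowhere written. Two surgeons could each follow the asymmetric-arm sentence faithfully and perform different totals. The reference list includes a work whose title speaks of augmented asymmetric recession, so the word asymmetric does not by itself imply an unchanged total. One added sentence would settle the matter at almost no cost, and Step 2 shows that the consequence could be large if the totals did differ.

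Much of this stands. The derivation is not spelled out, and an author who wished to spell it out would lose nothing. But it shows an incomplete description, not a stated rule that yields a wrong result. The harm needs a reading that the neighbouring sentence does not favour, and its size (12% to 97%) rests wholly on assumed inputs. The lack of a per-millimetre analysis is not an error. With equal totals it is not needed, and with unequal totals it swaps one untestable assumption for another.

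**Conclusion.** No change to the plan follows. This is a gap in description that the investigators can fill from the preceding sentence: the same angle, the same table and one amount divided differently. On that reading the difference in totals is 0 mm and the t test keeps its 5% level for the asymmetry question, taking correction to depend on the total and not on its division when asymmetry has no effect.

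If the totals proved to differ, randomisation would still make the t test a valid comparison of two surgical regimens. Only the attribution to asymmetry would fall away. That is a matter of reporting the millimetres performed in each arm and wording the conclusion to match, which a careful analyst would do in any case. The per-millimetre test is at best exploratory and could not carry a claim about asymmetry. How each eye's amount is derived is a matter for the investigators. All percentages depend on assumed values of PD per mm, SD, sample size, angle range and table amounts, none of which the documents give.

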# STATISTICAL ANALYSIS

Statistical analyses were performed using SPSS software version 17.0 (SPSS Inc, Chicago, IL). The pre- and postoperative values are described as means plus or minus standard deviations. The data were compared using the *t* test with a P value of < .05 was considered statistically significant.

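### The analysis plan states no adjustment for the preoperative angle; ANCOVA on it, with one named primary comparison, is a cheap efficiency gain whose size depends on an unstated correlation

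*Combined protocol and SAP*

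**What the plan says.** The analysis plan is the short STATISTICAL ANALYSIS section. It summarises the measurements ("The pre- and postoperative values are described as means plus or minus standard deviations") and then says "The data were compared using the *t* test", with significance at P < .05. It does not say which variable is tested, whether samples are paired or independent, or which comparison leads. It names no covariate.

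The rest of the document supplies the contrast. The INTRODUCTION states the intention that "we will compare long term motor and sensory effects of symmetric and asymmetric BLR recession", and AIM OF THE WORK frames the question as "Symmetric versus asymmetric bilateral lateral rectus recession". PATIENTS AND METHODS says "Patients will be randomized into two groups" and fixes the time point: "Outcome parameters at one year after surgery will be used for comparisons and analysis". So a comparison of S-BLR with A-BLR at one year is implied.

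The same section provides the covariate: "The angle of deviation at far and near is measured with the prisms and alternating cover test", before surgery, with the postoperative measurements made by the same method. It also defines a satisfactory outcome as alignment within 10 PD in either direction at one year, and it lists sensory testing by the Titmus and Worth 4-Dot tests.

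**The concern.** The trial collects a baseline value of its main motor outcome, on the same scale and by the same method, and the plan states no adjustment for it. Where baseline and outcome are correlated, adjusting for baseline removes variance that an unadjusted comparison leaves in, so the same patients give a narrower confidence interval. The data are already in hand.

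A related gap sits in the same sentence of the plan. Several one-year outcomes could lead the report, and none is named. ANCOVA does not settle that; naming one comparison does. In addition, a mean of signed deviations can hide recurrences and overcorrections that offset each other, so a comparison of mean angle cannot stand alone.

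**Working it through.** **Inputs.** The documents give no sample size, SD, effect size or pre-post correlation, so there is no figure of the plan to reproduce. Significance at .05 comes from STATISTICAL ANALYSIS. Assumed here: two-sided tests, 1:1 allocation, n = 10 to 50 per arm, and r = 0 to 0.7 between preoperative and one-year angle.

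**1. Confidence interval width, ANCOVA against a t test of the one-year angle alone.**

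Ratio = √(1 − r²) × E[√(1 + F/(2n − 2))] × t(.975, 2n − 3)/t(.975, 2n − 2), where F follows F(1, 2n − 2) and represents chance baseline imbalance.

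At n = 30 the expectation is 1.0088 and the quantile ratio is 2.0025/2.0017 = 1.0004, so the cost at r = 0 is 1.0088 × 1.0004 = 1.009. At r = 0.5, √0.75 = 0.866 and 0.866 × 1.009 = 0.874. The full set is:

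| n per arm | r = 0 | 0.2 | 0.3 | 0.5 | 0.7 | break-even r |
|---|---|---|---|---|---|---|
| 10 | 1.034 | 1.013 | 0.987 | 0.896 | 0.739 | 0.255 |
| 15 | 1.020 | 1.000 | 0.973 | 0.884 | 0.729 | 0.199 |
| 30 | 1.009 | 0.989 | 0.963 | 0.874 | 0.721 | 0.135 |
| 50 | 1.005 | 0.985 | 0.959 | 0.871 | 0.718 | 0.103 |

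Break-even is the r at which the ratio equals 1, that is √(1 − 1/K²) with K the ratio at r = 0.

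**2. Worst-case power loss.** Unadjusted power uses the noncentral t with 2n − 2 degrees of freedom and noncentrality d/√(2/n), where d is difference/SD. ANCOVA power uses 2n − 3 degrees of freedom and noncentrality d/[√(1 − r²) √(2/n) √(1 + F/(2n − 2))], averaged over F. At r = 0, the largest loss over any true difference is 2.75, 1.7, 1.2, 0.8 and 0.45 points at 10, 15, 20, 30 and 50 per arm.

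Illustration with an assumed difference of 5 PD, SD 8 PD and 30 per arm: d = 5/8 = 0.625 and noncentrality = 0.625/√(2/30) = 2.42. Power is 66.3% unadjusted. With ANCOVA it is 65.5%, 67.3%, 69.6%, 77.7% and 91.0% at r = 0, 0.2, 0.3, 0.5 and 0.7. In 100,000 simulated trials at r = 0, power was 0.662 unadjusted and 0.655 with ANCOVA.

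**3. If the intended t test is on change scores.** With equal preoperative and postoperative SDs, the variance of a change is proportional to 2(1 − r), and that of the ANCOVA residual to 1 − r². Their ratio is (1 − r²)/[2(1 − r)] = (1 + r)/2. That is 0.50, 0.60, 0.65, 0.75 and 0.85 at r = 0, 0.2, 0.3, 0.5 and 0.7, before the small cost of one covariate. Against this comparator ANCOVA gains at low r too.

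**4. No named primary.** In 20,000 null trials per setting (15 to 50 per arm, r 0 to 0.7), distance angle and near angle were each tested by ANCOVA. The proportion within 10 PD at distance was tested by an uncorrected chi-square (assumed mean 4 PD exo, SD 8 PD). The chance of at least one P < .05 was 11.5% to 13.9% with an assumed distance-near correlation of 0.5 to 0.8, and about 10% to 11.5% at 0.95.

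**5. Cancellation.** Take two arms with normally distributed angles, mean 0 PD, and SD 6 or 12 PD. The means are equal, but the share within 10 PD is P(|Z| < 10/6) = 90% in one arm and P(|Z| < 10/12) = 60% in the other.

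**The case against.** The strongest case against is that nothing here is wrong. Under randomisation an unadjusted between-arm t test is valid, and the gain rests on two quantities that the documents leave out. There is also a reason to expect a low r. In the S-BLR group "the amount of recession, based on the largest angle of exodeviation measured before surgery" determines the surgery, and operating more on larger angles tends to weaken the link between preoperative and one-year angle. At r = 0.2 and 30 per arm the interval is only about 1% narrower and power rises by 1 point (66.3% to 67.3%). At 10 per arm and r = 0.2 the interval is 1.3% wider. All of this stands, and it is why the point is an improvement only.

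A second objection is that widths, break-even values and power losses in steps 1 and 2 presuppose a t test of the one-year angle alone. The plan does not say so, and a change-score test is not ruled out. This also stands: those figures are conditional on that reading, and step 3 covers the other.

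A third is that the false-positive range uses tests that the plan does not name and an assumed correlation. The exact range does depend on these choices. The excess over 5% remains even at a distance-near correlation of 0.95.

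A reader might infer that the plan ignores the preoperative angle, that its t test is invalid, or that the trial will rest on within-arm before-and-after tests. The documents support none of these. Preoperative values are summarised, the angle guides surgery in the S-BLR group, and the aim, the randomisation and the one-year time point all imply a between-arm comparison.

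**Conclusion.** The point holds as a low-cost efficiency improvement, not as an error. The plan states no adjustment for a baseline angle that it already collects. Against a t test of the one-year angle alone at an assumed 30 per arm, ANCOVA ranges from a 0.9% wider interval at r = 0 to one 3.7% narrower at r = 0.3 and 12.6% narrower at r = 0.5. Break-even r is about 0.26, 0.20, 0.13 and 0.10 at 10, 15, 30 and 50 per arm. Against a change-score test with equal SDs the variance factor is (1 + r)/2. No large gain should be promised, because neither n nor r is given and r may be low.

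The benefit of naming one primary comparison does not depend on r. Under the assumptions shown, it holds the false-positive chance at about 5% instead of about 10% to 14%. On its own it is mainly a gap in specification, best closed in the same edit.

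**What to change.** In STATISTICAL ANALYSIS:

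1. Compare the one-year angle between S-BLR and A-BLR by ANCOVA with two terms, arm and the matching preoperative angle (distance for distance, near for near). Use one sign convention for exo and eso deviations. Report the adjusted mean difference with its 95% CI, and give the unadjusted t test as a sensitivity analysis.
2. Name one of the one-year outcomes in advance as the primary comparison. List the others as secondary, including the Titmus and Worth 4-Dot results. If the satisfactory-outcome proportion is chosen as primary, the ANCOVA becomes the secondary analysis of the angle.
3. Treat within-arm changes from before to after surgery as descriptive.
4. Whichever outcome leads, report the between-arm difference in satisfactory-outcome proportion with its 95% CI, because of the cancellation shown above.

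The cost is wording and one degree of freedom; no new data are needed. Against a t test of the one-year angle alone, the worst power loss at r = 0 is about 0.8 points at 30 per arm, 1.7 at 15 and 2.8 at 10. Below about 15 per arm with r expected under 0.2, adjustment brings no gain over that test, so the sponsor should weigh the planned sample size and settle the choice before outcome data are seen.
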